6.2.15 Hemolysis Calculation

Supernatant hemoglobin will be tested and % hemolysis calculated.

% Hemolysis will be determined according to the equation in Figure 5 and using Spun Hematocrit only.

Figure 5: Hemolysis calculation

$$\% \text{ Hemolysis} = \frac{(\text{Supernatant Hgb (mg/dL)} \times 0.001) \times ((1 - (\text{Hct} \times 0.01)) \times 100)}{\text{Total Hgb (g/dL)}}$$

6.2.16 Study Activities

Study donors who are eligible for study participation will be assigned to either the in vitro portion only or in vivo and in vitro groups. Study donors will be enrolled until the intended total of evaluable units has been collected. Note that cited days reference the number of days post collection.

See Tables 5-7 for summary of analyses and data collection.

Study Protocol

Clinical Investigation to Evaluate the New Health Sciences Hemanext® Oxygen Reduction System for Leukoreduced Red Blood Cells with CP2D Anticoagulant and AS-3 Additive - Pivotal Trial

Protocol #: CLIN-0001

Date: 28 Nov 2017

Page 27 of 65

- a) After signing the respective consent documentation, collect and record data relative to inclusion/exclusion criteria, demographics, concomitant medications and medical history.
- b) Collect and record the collection set's identification numbers.
- c) Collect a whole blood unit using the product per the IFU. Draw a sample of the study donor's native whole blood from the diversion bag and place aliquots in tubes for the indicated analyses.
- d) As soon as reasonably possible after collection, place anticoagulated whole blood units into room temperature storage until filtration.
- e) Immediately prior to filtration, weigh, sample and re-weigh each whole blood unit.
- f) Initiate room temperature filtration for each unit (5-7 hours post-collection). Record filtration-associated data.
- g) Weigh, sample and then re-weigh filtered whole blood units.
- h) As soon as practical following the completion of filtration, the LRWB units will be centrifuged and processed at room temperature to separate the unit into PRBCs and PPP. Record centrifugation-associated data.
- i) AS-3 will be mixed with the PRBCs as soon as practical following separation from the plasma.
- j) Following processing, the additive RBC unit will be weighed.
- k) Plasma will be discarded.
- l) The unit will be sampled and weighed.
- m) If the unit is in the CP arm then at this point it will be placed in refrigerated storage (1-6°C; within 8 hours of donation).
- n) If the unit is in the IP arm then the AS-3 LR-RBC unit will be transferred to the Hemanext ORB (within 8 hours of donation) at which point the unit will be weighed to ensure that the volume of the unit is less than 350 mL.
- o) The ORB will be placed on a Helmer Platelet Shaker for 3 hours + 15 minutes.
- p) The O₂ reduced LR-RBC will be transferred to the HSB at a head height of up to 72 inches at which point the unit will be sampled and weighed again prior to refrigerated storage (1-6°C; within 12 hours of donation) or on Day 1 until subsequent testing on Day 21 (+/- 1 day) and Day 42 (+ 1 day).
- q) For study participants participating in the in vivo portion of the study, refer to the instructions in section 6.2.11. Dual radiolabeled RBCs will

Study Protocol

Clinical Investigation to Evaluate the New Health Sciences Hemanext® Oxygen Reduction System for Leukoreduced Red Blood Cells with CP2D Anticoagulant and AS-3 Additive - Pivotal Trial

Protocol #: CLIN-0001

Date: 28 Nov 2017

Page 28 of 65

be infused on Day 42 and post-infusion blood samples will be drawn per local procedure. Study Participants will return to the site periodically on Days 43-70, and blood samples will be drawn per local procedure such that they are drawn within the time specified in Section 6.2.10.

- r) Study donors will return at \geq 56 days following their first donation. If the study donor continues to meet the inclusion/exclusion criteria, then they will donate their second unit of whole blood using product alternate to their randomization.
- s) Follow steps b) through m) if second unit is in the CP arm and follow steps b) through p) if second unit is in the IP arm..

Study Protocol

Clinical Investigation to Evaluate the New Health Sciences Hemanext® Oxygen Reduction System for Leukoreduced Red Blood Cells with CP2D Anticoagulant and AS-3 Additive - Pivotal Trial

Protocol #: CLIN-0001

Date: 28 Nov 2017

Page 29 of 65

Table 5: Procedure related data collection

		Donor	Collection		Leukoreduction		Separation	Post-Separation	
		Selection	(Pre)Collection	Pre-filtration	Filtration	Post-filtration	Centrifugation	Baseline	Day 0, 21, 42 Storage
Donor, Donation & Sample Handling Data Collection		WB	WB	WB	LRWB	LRWB		RBC + AS	RBC + AS
	Units / Blood Product	WB	WB	WB	LRWB	LRWB		RBC + AS	RBC + AS
			+ anticoagulant						
Study Donor	Date(s)	dd-MMM-yyyy	X					X	X
	Time(s)	hh:mm	X	X		X	X	X	X
	Temperature	°C / °F	X	X		X	X	X	
	IFU confirmation	Yes/No	X		X			X	
	Informed consent	Y/N, date, time	X						
	Eligibility criteria	See protocol	X						
	Demographics	See protocol	X						
	Concomitant Medications	Donor-reported	X						
	Medical History	Donor-reported	X						
Donation	Donation History	Donor-reported	X						
	Temperature	°C / °F	X						
	Blood pressure	mmHg	X						
	Pulse	BPM	X						
	System Manufacturer	See product		X					
	Part #/ Product code/ Lot #	See product		X					
Unit Handling	Collection date	dd-MMM-yyyy		X					
	Needle in	hh:mm:ss		X					
	Needle out	hh:mm:ss		X					
	Adverse Events	Donor-reported		X					
	Pre-sample Gross Weight	g			X	X		X	X
	Post-sample Gross Weight	g			X	X		X	X
	Filtration start/end time	hh:mm:ss				X			
	Filtration temperature	°C				X			
	Filter weight	g				X			
	Centrifuge details	See protocol					X		
	Centrifuge settings	See protocol					X		
	Hemanext Gross Weight	g						X	
	Hemanext Processing Start	hh:mm						X	
	Hemanext Processing End	hh:mm						X	
	HSB Gross Weight	g							X
	Refrigerator Date/Time/Temp	standard						X	X
	Bacterial culture notification (if needed)	dd-MMM-yyyy							X

Study Protocol

Clinical Investigation to Evaluate the New Health Sciences Hemanext® Oxygen Reduction System for Leukoreduced Red Blood Cells with CP2D Anticoagulant and AS-3 Additive - Pivotal Trial

Protocol #: CLIN-0001

Date: 28 Nov 2017

Page 30 of 65

Table 6: Specimen acquisition and analyses for IP arm

Specimen Acquisition, Analysis & Data Collection		Study Donor Selection-Pre-collection	Pre-filtration	Post-filtration	Baseline (Day 0)	Post-Hemanext (RBC Day0-1)	During Storage (RBC 20-22d)	Post-Storage (RBC 42-43d)
Units / Blood Product		WB	WB + Anticoagulant	LR WB	LR-RBC	LR RBC + AS-3	LR RBC + AS-3	LR RBC + AS-3
Hct/Hgb – finger stick	% / g/dL	x						
RBC Count	cells x 10⁶/µL		x	x	x	x	x	x
WBC Count	cells x 10³/µL		x	x	x	x	x	x
PLT Count	cells x 10³/µL		x	x	x	x	x	x
Hemoglobin	g/dL		x	x	x	x	x	x
Hematocrit	%		x	x	x	x	x	x
MCV	fL		x	x	x	x	x	x
MCH	pg		x	x	x	x	x	x
MCHC	g/dL		x	x	x	x	x	x
RDW	%		x	x	x	x	x	x
Spun Hematocrit	%		x	x	x	x	x	x
Sickle Cell Trait	+ / -	x						
Viral markers	+ / -	x						
ABO w/Rh factor	A/B/AB/O +/-	x						
Supernatant Hgb	mg/dL		x	x	x	x	x	x
ATP	µmol/L				x		x	x
2,3-DPG	µmol/L				x		x	x
ATP Rejuvenation	µmol/L							x
2,3-DPG Rejuvenation	µmol/L							x
rWBC Count	cells/µL			x				
SO₂	%				x		x	x
pO₂	mmHg				x		x	x
pCO₂	mmHg				x		x	x
HCO₃	mmHg				x		x	x
pH	at 37°C				x		x	x
Potassium	mmol/L or mEq/L				x		x	x
Sodium	mmol/L or mEq/L				x		x	x
Lactate	mmol/L or mg/dL				x		x	x
Glucose	mmol/L or mg/dL				x		x	x
RBC Morphology	0-100				x		x	x
RBC Deformability	MVA				x		x	x
RBC Microparticles	#MV (1000 beads⁻¹)				x		x	x
RBC Metabolomic Panel					x		x	x
Day 35-37 Bacterial culture	+/- (& notification)							x
Day 42 Pregnancy test	+/- (♀ only)							x
Day 42 In vivo recovery	%							x
In vivo Survival	%							x*

*Survival Calculated at 48h, 72h, 7d, 14d, 21d, 28d

Study Protocol

Clinical Investigation to Evaluate the New Health Sciences Hemanext® Oxygen Reduction System for Leukoreduced Red Blood Cells with CP2D Anticoagulant and AS-3 Additive - Pivotal Trial

Protocol #: CLIN-0001

Date: 28 Nov 2017

Page 31 of 65

Table 7: Specimen acquisition and analyses for CP arm

Specimen Acquisition, Analysis & Data Collection		Study Donor Selection-Pre-collection	Pre-filtration	Post-filtration	Baseline (Day 0)	During Storage (RBC 20-22d)	Post-Storage (RBC 42-43d)
Units / Blood Product		WB	WB	LR WB	LR-RBC	LR RBC + AS-3	LR RBC + AS-3
			+ Anticoagulant				
Hct/Hgb – finger stick	% / g/dL	x					
RBC Count	cells x 10⁶/µL		x	x	x	x	x
WBC Count	cells x 10³/µL		x	x	x	x	x
PLT Count	cells x 10³/µL		x	x	x	x	x
Hemoglobin	g/dL		x	x	x	x	x
Hematocrit	%		x	x	x	x	x
MCV	fL		x	x	x	x	x
MCH	pg		x	x	x	x	x
MCHC	g/dL		x	x	x	x	x
RDW	%		x	x	x	x	x
Spun Hematocrit	%		x	x	x	x	x
Sickle Cell Trait	+ / -	x					
Viral markers	+ / -	x					
ABO w/Rh factor	A/B/AB/O	+/-	x				
Supernatant Hgb	mg/dL		x	x	x	x	x
ATP	µmol/L				x	x	x
2,3-DPG	µmol/L				x	x	x
ATP Rejuvenation	µmol/L						x
2,3-DPG Rejuvenation	µmol/L						x
rWBC Count	cells/µL			x			
SO₂	%				x	x	x
pO₂	mmHg				x	x	x
pCO₂	mmHg				x	x	x
HCO₃	mmHg				x	x	x
pH	at 37°C				x	x	x
Potassium	mmol/L or mEq/L				x	x	x
Sodium	mmol/L or mEq/L				x	x	x
Lactate	mmol/L or mg/dL				x	x	x
Glucose	mmol/L or mg/dL				x	x	x
RBC Morphology	0-100				x	x	x
RBC Deformability	MVA				x	x	x
RBC Microparticles	#MV (1000 beads⁻¹)				x	x	x
RBC Metabolomic Panel					x	x	x
Day 35-37 Bacterial culture	+/- (& notification)						x
Day 42 Pregnancy test	+/- (♀ only)						x
Day 42 In vivo recovery	%						x
In vivo Survival	%						x*

*Survival Calculated at 48h, 72h, 7d, 14d, 21d, 28d

Study Protocol

Clinical Investigation to Evaluate the New Health Sciences Hemanext® Oxygen Reduction System for Leukoreduced Red Blood Cells with CP2D Anticoagulant and AS-3 Additive - Pivotal Trial

Protocol #: CLIN-0001

Date: 28 Nov 2017

Page 32 of 65

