5.0 Study Design / Analysis

5.1 Study Design

In vitro and in vivo performance of O₂/CO₂ reduced red blood cells produced with the Hemanext System will be used to demonstrate the acceptability the final product for clearance. To accomplish this, the study will require a total of 100 study donors. The study entails a randomized, paired, 2-x-2 crossover design where every study donor (n = 100) who completes the study will donate a total of two whole blood units with individual units being donated at least 56 days (8 weeks) apart. One unit will be used as the test and the other unit will be used for the control. The order in which the IP and the CP will be used to collect, filter and store the whole blood and appropriate blood products (within the context of the crossover design) will be randomized.

The full clinical investigation is summarized in Table 2. See the study's flow diagram in **Section 13.1** for an additional reference.

Table 2: Hemanext™ Clinical Trial Design Summary

Hemanext Pivotal Clinical Trial Summary	
‘n’ (evaluable) *	93
Pre-filtration storage & filtration conditions	20-24°C
Randomized, Paired, Crossover	Investigational unit filtration <8 hours + up to 4 hours processing
	Control unit filtration < 8 hours
In vivo subgroup study (‘n’)	√ (24-28)
Post-filtration assessments	√
Baseline assessments	√
Post-storage assessments	√

Study Protocol

Clinical Investigation to Evaluate the New Health Sciences Hemanext® Oxygen Reduction System for Leukoreduced Red Blood Cells with CP2D Anticoagulant and AS-3 Additive - Pivotal Trial

Protocol #: CLIN-0001

Date: 28 Nov 2017

Page 14 of 65

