6.2.6 Slow Filtrations

Any filtration with a Bag Empty Time (emptying of the Donor Bag) that is greater than one hour will be considered a slow filtration. Slow filtrations will be documented, the Sponsor will be notified immediately and testing will continue to completion if the product is stored in < 12 hours for the IP or < 8 hours for the CP groups.

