9. Hang AS-3 bag above red cell storage bag and remove clamp from tubing to the red cell storage bag.

10. Open snap-open closure on the bag containing the AS-3 additive solution and transfer to the bag containing the red cells.

Note: AS-3 solution should be added to the packed red blood cells immediately after removal of plasma. Transfer AS-3 solution under one of the following processing conditions:

a. within 8 hours of collection if whole blood is held at room temperature.

b. within 72 hours of collection if whole blood is refrigerated.

11. Seal tubing and detach the bag containing packed red cells, and set aside plasma for further processing.

** **Note:** If quality control is to be performed on post filtration sample, leave an adequate length (~10 inches) of tubing attached to the bag containing red cells.

12. Gently mix packed red cells and AS-3 solution.

13. Store CP2D/AS-3 preserved red blood cells at 1—6 °C for up to 42 days and use as indicated.

Note: If AS-3 is not used, whole blood or red blood cells in CP2D alone may be stored at 1-6 °C for up to 21 days.

147126927, issued Jul. 2010

* WBF2

** During processing, always observe the following precautions:

1. Sealing should be done in a manner that avoids fluid splatter.
2. Always dispose of blood-contaminated products in a manner consistent with established BIOHAZARD safety procedures.

Study Protocol

Clinical Investigation to Evaluate the New Health Sciences Hemanext® Oxygen Reduction System for Leukoreduced Red Blood Cells with CP2D Anticoagulant and AS-3 Additive - Pivotal Trial

Protocol #: CLIN-0001

Date: 28 Nov 2017

Page 60 of 65

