13.3 Investigational Product/Hemanext RBC Processing System – Instructions for Use
Hemanext™ RBC Processing System

CAUTION – Investigational Device. Limited by Federal (or United States) Law to Investigational Use.

DEVICE DESCRIPTION:

Blood container set used to process and store CP2D/AS-3 Red Blood Cells, Leukocytes Reduced, and O₂/CO₂ Reduced.

Each system consists of:

- One Oxygen Reduction Bag (ORB): empty oxygen impermeable container for processing of CP2D/AS-3 Red Blood Cells, Leukocytes Reduced.
- One Hemanext Storage Bag (HSB): empty oxygen impermeable container for storage of CP2D/AS-3 Red Blood Cells, Leukocytes Reduced, and O₂/CO₂ Reduced.
- One LR RBC blood line
- Three flow control blood line clips

Study Protocol

Clinical Investigation to Evaluate the New Health Sciences Hemanext® Oxygen Reduction System for Leukoreduced Red Blood Cells with CP2D Anticoagulant and AS-3 Additive - Pivotal Trial

Protocol #: **CLIN-0001**

Date: 28 Nov 2017

[figure not shown]
Page 61 of 65

Figure 1: Hemanext RBC Processing System

Study Protocol

Clinical Investigation to Evaluate the New Health Sciences Hemanext® Oxygen Reduction System for Leukoreduced Red Blood Cells with CP2D Anticoagulant and AS-3 Additive - Pivotal Trial

Protocol #: CLIN-0001

Date: 28 Nov 2017

Page 62 of 65

INDICATIONS FOR USE:***Blood container set used to process and store Red Blood Cells Leukocytes Reduced, O₂/CO₂ Reduced.***

The Hemanext system is intended to process and store CP2D/AS-3 Red Blood Cells, Leukocytes Reduced that have been prepared within the standard 8-hour hold time. The Red Blood Cells will be processed using the Hemanext system within 12 hours of collection. The Hemanext RBC Processing System limits the O₂ and CO₂ levels in the storage environment. Red Blood Cells Leukocytes Reduced, O₂/CO₂ Reduced may be stored for up to 42 days at 1-6°C. The Hemanext RBC Processing System is used for volumes no greater than 350 ml of LR RBC.

CONTRAINDICATIONS:

- Sickle Cell Trait blood cannot be used for Hemanext RBC processing.

PRECAUTIONS:

- The Hemanext RBC Processing System is not intended for manufacture of red blood cells using other additive solutions than AS-3.
- Not intended for non-leukocytes reduced red blood cells.
- Not intended for processing of apheresis red blood cells.
- Dispose of used components using acceptable biohazard disposal methods.
- Units must be used within 24-hours of opening individual packaging.

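### A late start in the 5–7 hour filtration window leaves too little time for the 8-hour limits, and the slow-filtration rule does not repeat the 8-hour ORB limit for test units

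*Combined protocol and SAP*

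**What the plan says.** Section 6.2.16 sets the sequence for every unit.

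- **Step f:** "Initiate room temperature filtration for each unit (5-7 hours post-collection".
- **Steps g–l:** weighing and sampling, centrifugation, plasma separation, addition of AS-3, then further weighing and sampling. No durations are given.
- **Step m (control, CP):** "it will be placed in refrigerated storage (1-6°C; within 8 hours of donation".
- **Step n (test, IP):** "transferred to the Hemanext ORB (within 8 hours of donation".
- **Steps o–p (test only):** about 3 hours of agitation, transfer to the storage bag, and refrigeration within 12 hours of donation.

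Section 6.2.6 defines a slow filtration as a Bag Empty Time above one hour. Testing of a slow unit goes on "if the product is stored in < 12 hours for the IP or < 8 hours for the CP groups".

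Other places set related limits.

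- **Table 2 (section 5.1):** "Investigational unit filtration <8 hours + up to 4 hours processing" for the test unit, and filtration under 8 hours for the control unit.
- **Leukotrap instructions (13.2):** AS-3 is to be added "within 8 hours of collection if whole blood is held at room temperature".
- **Hemanext indication (13.3):** "Leukocytes Reduced that have been prepared within the standard 8-hour hold time", with Hemanext processing inside 12 hours of collection.

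Under 5.3.5.1, a procedural deviation that the investigator and/or sponsor judges able to affect an endpoint makes the collection non-evaluable. Slow filtration is not itself on that list.

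**The concern.** There are two separate problems.

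First, the permitted start time and the permitted filtration time can together use up the whole 8 hours before centrifugation begins. A site can keep to step f and to 6.2.6 and still miss step m or n. It also cannot tell which event the 8 hours governs, because the documents attach it to filtration, AS-3 addition, preparation of the leukoreduced red cells, refrigeration and ORB transfer.

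Second, handling is the same in both arms through step l, yet for slow filtrations 6.2.6 checks the arms at different points. The control unit is checked directly after the shared steps. The test unit is checked only after its extra processing, against 12 hours, with no mention of the 8-hour ORB limit.

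Three things are at stake:

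- **Matched pairs.** Under 5.3.2 an evaluable donor completes two Day 42 periods, so losing one unit costs the pair.
- **Between-arm comparisons.** Section 5.4 lists these as secondary, and retained units could differ in upstream hold time.
- **Processing conditions.** Some test units may fall outside those the plan states.

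**Working it through.** **The plan's own figure.** Table 2 gives 8 h + 4 h = 12 h for the test unit. This matches the 12 h in step p and in 6.2.6, so the total is consistent. The question is what happens inside the first 8 hours.

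**1. Time budget to 8 hours**

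Inputs:
- start S = 5 to 7 h (step f);
- filtration F, not slow up to 1 h (6.2.6);
- handling P for steps g–l. This is not stated, so I assume 0.25 to 2 h.

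I treat time from collection and time from donation as one clock.

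Condition: S + F + P ≤ 8 h, so latest start = 8 − F − P.

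Time left at the start of filtration is 3 h for S = 5, 2 h for S = 6 and 1 h for S = 7. At S = 7 and F = 1 h, 8 − 7 − 1 = 0 h remains for steps g–l. This result needs no assumption about P. Bag Empty Time also covers only the emptying of the donor bag. The Leukotrap instructions still require the filter to drain afterwards, and drain time is recorded separately (6.2.16.5).

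Share of the window that works = (latest start − 5) / 2, capped at 100%:

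| P (assumed) | Latest start, F = 1 h | Share, F = 1 h | Latest start, F = 0.5 h | Share, F = 0.5 h |
|---|---|---|---|---|
| 0.25 h | 6.75 h | 87.5% | 7.25 h | 100% |
| 0.5 h | 6.5 h | 75% | 7.0 h | 100% |
| 1 h | 6.0 h | 50% | 6.5 h | 75% |
| 1.5 h | 5.5 h | 25% | 6.0 h | 50% |
| 2 h | 5.0 h | 0% | 5.5 h | 25% |

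These are shares of clock time, not of units. The documents give no distribution of start times.

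**2. Slow filtrations only**

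Inputs:
- agitation A = 3 h 15 min at the top of step o, or 2 h 45 min to 3 h 15 min in the Hemanext instructions;
- transfer and sampling T after agitation. This is not stated, so I assume 0 to 0.5 h.

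The ORB start that still allows storage in under 12 h must fall before 12 − A − T. Minutes past the 8-hour ORB limit:

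| A | T = 0 | T = 0.25 h | T = 0.5 h |
|---|---|---|---|
| 2 h 45 min | 75 | 60 | 45 |
| 3 h | 60 | 45 | 30 |
| 3 h 15 min | 45 | 30 | 15 |

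Example: two slow units are both ready at 8:24. The test unit goes 8:24 + 3:15 + 0:15 = 11:54, which is under 12 h, so testing continues although step n was missed. The control unit is already past 8 h and fails its condition.

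The margin is narrow. A unit loaded at 8:30 with 25 min for transfer and sampling is stored at 11:55 after 3 h of agitation, but at 12:10 after 3 h 15 min, and then fails.

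**3. Acceptance rule**

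P(at most 1 failure in 93 at a 5% failure rate) = 0.04998. For 92 units it is 0.0521. The 93-unit, one-failure rule reproduces, and neither problem changes it.

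**The case against.** The strongest reply is that step f and steps m/n apply together: one gives a permitted start range, the other a binding end, and a competent site will start early enough to meet both. Detail may sit in the Operations Manual and site procedures, which are not available here. The 12-hour and 8-hour figures in 6.2.6 repeat the storage limits of steps p and m, which differ because the test arm has an extra step of about 3 hours. Table 2 is a summary and may be shorthand. The primary criteria are pass/fail on test units, and lost donors may be replaced.

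Much of this stands, and it rules out two stronger readings.

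- A reader might infer that the window cannot meet the 8-hour limits at all. It can. A 5-hour start leaves 3 hours, and even a 7-hour start works if F + P is at most 1 hour. Missing step m or n does not by itself breach either set of instructions either, because AS-3 is added at step i, before steps j–l.
- A reader might infer that 6.2.6 keeps late test units in the primary data set and drops late control units. It says neither. It gives a condition for continued testing, does not say what happens to a unit that fails it, and does not waive step n. It also does not cover a unit that started near 7 hours and drained within one hour.

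The reply does not remove the zero margin at a 7-hour start with a 1-hour filtration, the several events tied to 8 hours, or the missing ORB check in 6.2.6.

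**Conclusion.** The point holds in limited form. The late part of the window conflicts with the 8-hour limits. At the 7-hour end with the longest filtration not classed as slow, the conflict follows from the stated times alone. How much of the window is affected depends on unstated handling time: with a 1-hour filtration, from 12.5% at P = 0.25 h to all of it at P = 2 h.

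For slow filtrations, a test unit about 15–75 minutes late into the ORB, depending on assumed agitation and transfer times, can meet the continuation condition where an equally late control unit does not. That test unit is still a step n deviation, and its evaluability is left to investigator and/or sponsor judgement without a stated time rule. No expected number of affected units can be given.

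The effect is on retained pairs, secondary comparisons and conformity of test units with the stated processing conditions, not on the acceptance rule.

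**What to change.** 1. Reconcile Table 2, section 6.2.6, section 6.2.16 steps f and m–p, and the two instructions for use, so that the 8-hour limit is tied to one stated event. I take no view on which event or limit is right.
2. In step f, derive the latest filtration start from whichever limit governs, less the 1-hour filtration allowance and the site's measured time for steps g–l.
3. In 6.2.6, apply the same upstream check to both arms, with the test arm's storage limit as an additional test.
4. State in 5.3.5.1 the evaluability of units that miss the upstream check, in identical terms for both arms.

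The cost is protocol wording and a narrower start window for site scheduling. The key times are already collected: filtration start and end, AS-3 addition, agitator on and off, and refrigeration. Time on the agitator is the nearest listed record of ORB transfer, so the check should say whether it serves as the proxy.
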